The DELTA Study requires this considerable effort to standardize blood collection, processing, and storage, since it involves four U.S. field centers. This protocol is necessitated by the importance of all sample collection procedures being feasible and of high quality in order to meet all the investigators' needs. This protocol is derived, in part, from that developed by [name]., for the Cardiovascular Health Study, for which the University of Vermont serves as central laboratory.

B. Laboratory Organization

The laboratories involved in the protocol will consist of those affiliated with the field centers, including Columbia University (CU), Louisiana State University (LSU), Pennsylvania State University/The Mary Imogene Bassett Research Institute (MIBH), and the University of Minnesota (UM), as well as the central coagulation laboratory at the University of Vermont (UV) ([name].).

II. SAMPLE COLLECTION -- AN OVERVIEW.

A. Overview.

Table 1 (see Appendix I for tables) provides a summary of the samples to be collected for endpoint analysis. DELTA Study requires collection of approximately 41 ml of blood three times at the end of each diet phase. In addition participants will be asked to collect a first morning urine each of the last two weeks of each diet phase. Some participants may be asked to participate in postprandial studies which involve additional collection of 14 to 34 mL of blood on each of those days. Since the study depends on the voluntary participation of subjects, both initially and in follow-up, every effort must be made to make the entire procedure as easy and painless as possible, both for the participants and for the field center personnel.

The endpoint package contains a serum and urine for routine endpoint tests. These are outlined in Table 2. Sample requirements and disposition of samples for special tests are outlined in Table 3. Sites of analysis are given in Table 4.

For the endpoint package, any participants who are concerned about the volume of blood should be reassured that the total amount of blood is 1/15th of the volume given in a typical Red Cross blood collection (450 ml). Each endpoint package should be collected after an 8-hour fast with sample collection occurring between 7-10 a.m.

The processing requirements of for all samples except the postprandial studies are shown in Table 5. The collection and processing of the samples for the postprandial studies are given in Table 6.

B. Blood Collection Trays and Tubes.

1. Blood Collection Tray.

Blood collection trays are prepared in advance for the following day. Each tray is stocked with a full supply of blood-drawing equipment for three to four participants and holds individual blood collection racks for each participant in an ice bath. Several racks are prepared to hold various plastic tubes and vials for the final serum and plasma aliquots. The blood collection tube rack and aliquot tube rack are pre-labeled with the appropriate code numbers for the participants drawn that day.

2. Blood Collection Rack.

The collection tray itself is made of hard plastic which is unbreakable and can be easily cleaned. The tray has 10 individual compartments which will be filled with the following supplies:

- 21 g butterfly needles with luer adapter
- alcohol swabs
- Band-Aids
- Gauze
- Tourniquets (2)
- Vacutainer holders
- Needle/Sharps container
- Smelling salts
- Timer/Stop watch
- Scissors
- Adhesive tape
- Styrofoam ice bath filled approximately
10 minutes before draw
- Pencils/Pens
- Latex gloves
- Test tube racks (2)

A separate rack contains the necessary draw tubes, etc. for each participant. The tubes are arranged according to the priority of the draw. This rack will fit into the blood collection tray. The blood collection tubes are pre-labeled with identification numbers.

3. Description of blood collection tubes for endpoint package.

Tubes 1 and 6 are a 10 ml siliconized yellow/black stopper tube. This tube contains thrombin so that the blood clots to form serum in 5 minutes. Aliquots are coded red. This serum is used for the lipid profiles, glucose, insulin, and apoproteins.

Tube 2 is a 4.5 ml blue-top tube containing 0.5 ml of 3.8% sodium citrate. It is crucial that this tube remain at room temperature. After centrifugation, plasma is aliquoted into green-coded aliquots. The plasma will be used for Factor VII coagulation assay. This tube will be used to provide seven 3-uL aliquots for platelet activation in week 7.

Tube 3 is also a 4.5 ml blue-stopper tube identical to Tube 3. It is different in the way it is processed. Instead of room temperature, this tube must be placed on ice after filling. Plasma from this tube is aliquoted into blue-coated aliquots and will be used for fibrinogen assay and PAI-1 assay.

Tube 4, identified as a Diatube, is a 5-ml blue top tube with a red label. It contains special stabilizers. It should be kept cold prior to the blood draw. It is recommended that it be chilled on ice at least 15 min before use. This tube will be collected on weeks 5 and 6 only. It must be placed on ice immediately after collection. The plasma from this tube is filtered and the filtered plasma is will be used for measurement of beta-thromboglobulin. These tubes may be purchased from the University of Vermont ([name]) or directly from American Bioproducts Company ([name]; Ph. [contact])

Tube 5 is a 7.0 ml purple stopper tube. This tube requires mixing after filling and placement on ice. After centrifugation, plasma is aliquotted into yellow-coded cryovials (0.5 ml). The plasma will be used for ancillary and supplemental studies.

Each draw tube is assigned a color-coated aliquot system. There is one type of aliquot used: 0.5 ml cryovials. The cryovials have colored caps.

4. Priority of tubes.

A total of approximately 41 ml will be drawn from each participant in five tubes at each endpoint package. The tubes are drawn in priority order.

The tubes are numbered 1-6. 1-2 and 6 are in a room temperature rack. Tubes 3, and 5 are kept on ice.

5. Forms.

a. Purpose:

The purpose of the blood collection form is to facilitate the collection of plasma and serum samples from participants. This collection must be done in a rapid and efficient manner, with maximum protection for the participant. In addition, the process must facilitate the monitoring of phlebotomy and other quality assurance parameters as well.

Note: All forms are to be completed in ink.

b. Description:

There are two parts of the Phlebotomy Processing Form associated with blood drawing. The top half is the participant/phlebotomy question about fasting status. If the person has eaten less than eight hours earlier, he/she should be rescheduled on an alternate day, within three days of the initially scheduled date.

The bottom half deals with phlebotomy and processing of samples.

These forms have the following purposes: 1) Assure the most efficient and safest possible venipuncture for participants. 2) Allow the monitoring of the quality of the above procedures. 3) Allow more efficient processing of the samples at central laboratories. 4) Provide information critical to the interpretation of assay results.

III. PROCESSING THE BLOOD SAMPLES

A. General:

Processing should be done immediately following venipuncture. Personal protective equipment (non-permeable lab coats, double gloves with at least one Latex pair, spatter shield) must be worn. Flowchart is included at the end of this section to diagram this process (Figure 2).

B. Immediate Processing of Endpoint Samples:

Upon reaching the blood processing station, remove the blood tube drawing rack and ice bath containing tubes from the blood collection tray. The rack should contain three tubes: #1, #2, #6. The ice bath should contain three tubes: #3, #4, #5. All tubes should be processed within 30 minutes of phlebotomy. The corresponding aliquot racks (two per patient) should be ready. Rack #1 (with color codes blue, clear and purple) should be placed in an ice bath. Rack #2 (with color codes red and green) remains at room temperature.

C. Centrifugation:

Tubes #3, #4, and #5 are centrifuged at 4°C for 10-20 minutes at 3,000 g. The centrifuge may need to be precooled to 4°C. 4.5 ml, 5 ml, and 7 ml balance tubes are required for tubes #3, #4 and #5. Simultaneously, tubes #1, #2 and #6 are centrifuged at room temperature for 10-20 minutes at 3,000 g. A 4.5-ml balance tube may be required for tube #2. Once centrifuged, the maximum time allowed before aliquoting is 10 minutes. While these tubes are spinning, the blood collection tray can be restocked with tube rack and blood collection tubes, ice, and forms for the next participant. Recheck labels on the two aliquot racks. Perform any necessary clean-up.

D. Aliquots:

Allow the centrifuge(s) to come to a complete stop. Remove tubes from the refrigerated centrifuge and place in an ice bath, being careful not to shake the tubes. Remove tubes from the room temperature centrifuge. Place in tube rack at room temperature. Assess the plasma. Mark o. the Phlebotomy Processing Form if lipemic (L), icteric (I), hemolyzed (H), clotted (C). Follow the

outline on the Phlebotomy Processing Form for aliquoting the samples. Checkmark on the form if the aliquot is completed, and mark any different volumes. Be careful not to disturb the other white cell layers. If plasma is a lower than expected volume, use one less aliquot rather than disturb the red cells or buffy coat. Do not have any red cells in the aliquots. Use a new pipette tip for each tube type. Recap aliquots after each draw tube has been pipetted.

		ALIUQUOT
Tube #5	Use 500 uL MLA Cryovials (6) - 0.5 mL plasma/cryovial	Rack 1 (on ice) Lavender code
Tube #3	Use 500 uL MLA Cryovials (4) - 0.5 mL plasma/cryovial	Rack 1 (on ice) Blue code
Tube #2	Use 500 uL MLA Cryovials (4) - 0.5 mL/cryovial	Rack 2 (room temp.) Green code
Tube #1	Use 500 uL MLA pipette Cryovials (7) - 0.5 mL serum/cryovial	Rack 1 (on ice) Red code
Tube #6	Use 500 uL MLA pipette Cryovials (7) - 0.5 mL serum/cryovial	Rack 1 (on ice) Red code
Tube #4	Transfer 1 ml of plasma into a 3-ml syringe that has an Acrodisc attached. Gently push the plasma through the filter into the cryovial - placing one half in each of 2 cryovials.	Rack 1 (on ice) Clear code

Checkmark on the Phlebotomy Processing Form if the aliquot is complete, then mark any different volumes. Original blood collection tubes can be properly disposed of in biohazard waste bags.

E. Freezing:

Upon completion of the processing steps, aliquots must be frozen within 10 minutes. Green aliquots (4 cryovials) at room temperature are added to the rack at 4°C. That rack is removed from the ice bath and placed upright in the freezer at -80°C for at least ½ hour (preferably until the end of the day). Make sure the aliquots are not wet when they are placed in the freezer. If the -80°C freezer is not immediately available, the aliquots can be placed on dry ice or snap frozen in liquid nitrogen/methanol mixture.

F. Completed Forms:

The completed Phlebotomy Processing Form can be set aside in the daily work folder. Originals are filed at each field center; the copy will be sent to the University of Vermont when samples are shipped.

G. End of the Day Procedures:

Frozen aliquots and racks are packaged with pre-labeled freezer box. One box contains the aliquots from a single endpoint series on each patient (30) aliquots per total). The boxes containing aliquots are stored at -80°C freezer by date. The copy of the Phlebotomy Processing Form is kept in a file to be included with the shipment of samples. Restock blood collection tray with samples. Label with next day's participants. Blood draw tubes, aliquots, forms. Arrange draw tubes and aliquots in their proper racks. Wipe down all work areas with 10% Clorox solution.

H. Summary of Processing Time Limitations:

On blood drawn prior to processing:

- 1) Serum 10 ml - 40 minutes;
- 2) Citrate 4.5 ml - room temperature - 30 minutes;
- 3) Citrate 4.5 ml - 4°C - 30 minutes;
- 4) Diatube 5.0 ml - 4°C - 30 minutes;
- 5) EDTA 7.0 ml - 4°C - 30 minutes;
- 6) Serum 10 ml - 40 minutes;

Once centrifuged, maximum time before aliquoting is 20 minutes; after aliquoting all samples, freeze within 30 minutes.

IV. URINE COLLECTION

Urine samples will be collected the mornings of two scheduled blood draws per diet period (weeks 6,7). Participants should be provided a plastic bottle (labeled with the subject ID number) the day before with instructions (See Appendix II) to collect the first urine sample when they get up the next morning. This sample should be brought to the lab when they arrive for the drawing of their blood sample. Note the receipt of the sample on the Urine Collection Form (Appendix II).

Before aliquoting, mix the sample by swirling the bottle. Remove the cap. Aliquot 2 ml in each of five 2-ml cryovials pre-labeled with the subject ID. Place yellow caps on these samples and freeze at -80°C .

V. POSTPRANDIAL BLOOD COLLECTION AND PROCESSING

The processing of samples for the postprandial studies is summarized in Table 6.

A. Regular diet

When the subject returns before lunch and before dinner, one 7-ml red top tube is drawn. This tube should sit at room temperature for at least 45 minutes to allow the blood to clot. The tube is then centrifuged for 30 minutes at 4°C at 3000xg.

Four 0.5 ml aliquots of serum are placed into four cryovials labeled with the subject ID and coded for the appropriate time point for this postprandial study. Each vial is capped with a red cap and frozen at -80°C .

B. Fat load

Each subject will return at 4 and 8 hours after consuming the fat load. Two tubes of blood are drawn at each time - a 7-ml red top tube (serum) and a 7-ml purple top tube (EDTA plasma) and a 4.5-ml blue top (citrate plasma). The purple top tube must be protected from light to prevent degradation of these compounds; if they will not be processed immediately, they should be wrapped in foil.

Red top tube

The red top tube should be allowed to sit at room temperature for 45 minutes to clot. The tube is then centrifuged for 30 minutes at 4°C at 3000xg.

Four 0.5 ml aliquots of serum are placed into four cryovials labeled with the subject ID, and coded for the appropriate time point for this postprandial study. Each vial is capped with a red cap and frozen at -80°C.

Purple top tube

The purple top tube should be placed in an ice bath immediately after drawing and kept at 4°C until centrifugation. Centrifugation is for 30 min at 4°C at 3000 x g. Two 1-ml aliquots of plasma are transferred to 3.7-ml amber vials (Fisher Scientific cat.# 03-339-23B). A gentle stream of nitrogen is layered on top of the plasma and the vials are capped and frozen at -80°C.

It is vital that the plasma be protected from light. If the transfer is not immediate to the amber vials, the plasma tubes should be wrapped in aluminum foil until transfer. Transfer should occur with room lights dimmed.

Blue top tube

The blue top tube should be kept at room temperature. Centrifugation is for 30 min at room temperature. Two 0.5-ml aliquots should be transferred to cryovials with green caps. These aliquots should be placed at -80°C immediately after separation from red cells.

C. Sample Preparation for Retinyl Ester Determination

Blood to be used for retinyl ester determination will be drawn in to EDTA containing tubes (lavender top) wrapped with aluminum foil to protect the sample from light. Isolation of plasma can be done following the usual centrifugation protocol for lavender top tubes. When plasma is transferred into aliquot vials, the room should be dim. Plasma to be used for determination of retinyl ester levels is stored under nitrogen at -70°C until assayed.

The aliquot vials are from Fisher Scientific, Cat # 03-339-23B. They have a capacity of 3.7 mls, are 15 x 45 mm, and have rubber-lined closures. A pack of 144 vials is \$39.00. For 25 subjects, keep 2 samples per fat load test (4 and 8 hrs.) x 3 diets = 150 vials. Each center will need 2 packs of vials.

D. Retinyl ester determination

Plasma retinol and retinyl ester (retinyl palmitate, retinyl stearate, retinyl linoleate and retinyl myristate) levels will be measured by reverse phase high-performance liquid chromatography (HPLC). This procedure employs an internal standard technique for the calculation of retinal and retinyl ester levels. The within-assay and between-assay coefficients of variation of retinol and retinyl ester determination are less than 7 percent.

For retinoid determinations, 100 μ l serum or plasma will be denatured by addition of 100 μ l ethanol containing internal standard retinyl acetate, and the retinoids will be extracted into hexane. The hexane extract will be backwashed with H₂O, evaporated to dryness under a gentle stream of nitrogen, and redissolved in benzene for injection onto the HPLC column. Chromatography will be carried out on a 4.6 x 25 mm Beckman 5 μ Ultrasphere ODS column using 70% acetonitrile-15% methanol as solvent. Flow rate will be 2.0 ml/min. Retinol and retinyl esters will be detected by absorbance at 325 nm. Levels will be determined from a standard curve relating integrated peak area ratios of the retinoid of interest and the internal standard retinyl acetate to mass ratios of the two compounds. Standard curves will be constructed using authentic retinol, retinyl palmitate, retinyl stearate, retinyl oleate, retinyl linoleate and retinyl myristate which will be obtained either commercially (retinyl palmitate and retinol) or in the laboratory of [name].

All HPLC procedures will be carried out on equipment obtained from Waters Associates. This includes 2 Model 6000 pumps, a WISP Model 710 Autosampler, a Model 7230 System Controlled, a Model 730 Data Module, and a Model 480 variable wavelength UV detector. This HPLC system is fully automated and is regularly used to determine serum and tissue retinoid levels.

VI. STORAGE OF ALIQUOTS

Blood samples sent to Field Lipid Laboratories and central laboratories will be stored at -80°C until analyzed.

Numerous additional aliquots are to be stored at the Field Centers for later analyses, as yet not proposed. The rationales for using the Field Centers for storage:

1. This reduces the risk of loss of endpoint samples, since some samples would be retained by the Field Centers,
2. The laboratories analyzing these samples are as yet unknown, and they could be shipped directly at the time needed.

Each Field Center should identify a -80°C freezer which is protected from thawing through a reliable alarm system or back-up power system. The loss of aliquots through thawing may result in exclusion of that center's samples from important analyses.

A software program will be developed for the purpose of inventory control. The maintenance of this inventory is the responsibility of the field centers. All samples collected, stored,

and shipped shall be accounted for on this program. Training on the use of the program will be included in the training sessions.

VII. SHIPPING AND RECEIVING SAMPLES

A. General:

Samples are stored at the field centers at -80°C and shipped to the various laboratories according to the schedule in Table 7.

B. Packaging for shipping:

The samples to be shipped are removed from boxes stored at -80°C and packaged in bags for each subject and be accompanied by a shipping list that identifies the samples being sent.

The styrofoam mailer is lined with absorbent material; i.e., paper towels. Approximately half the dry ice is placed on the bottom of the mailer. Check the ID number against the transmittal form. Carefully place the zip-lock bags, each containing the samples from a single subject, in the mailer. Remaining dry ice (6 pounds total) is placed on the sample. The top of the styrofoam is sealed up with tape. It is closed with the outer cardboard sheath. The paperwork is placed on top of the styrofoam before the outer sheath is closed by tape or strap. Fix shipping labels. Place the entire box in the refrigerator if pick-up is not immediate (samples should not be on dry ice for more than 24 hours). Note: The number of samples per box may vary depending on the size of the container used. We recommend using your judgment and 6 pounds of dry ice.

C. Sample Shipping Checklist:

- Styrofoam mailing container with outer cardboard sleeve
- Absorbent material
- Zip-lock bag
- Packaging tape
- Dry ice (6 pounds per shipment)
- Labels (provided by carrier)
- Completed Phlebotomy Processing Form
- Blood sample transmittal form

D. Shipping and receiving communications:

Details of which samples are to be shipped to each center and the specific addresses for these samples will be provided at the time the samples are to be shipped.

Samples received at central laboratories will be preceded by a FAX of the transmittal form. Upon receipt of the shipment, the transmittal form is checked against the fax, to assure that no confusion has occurred and to allow for telephone verification if there are any lingering doubts. The samples are removed from the package and immediately transferred to a -80°C freezer for later analyses. Any problems in the shipment in terms of thawing, breakage, etc. should be noted.

Samples are thawed prior to analyses per protocol, either at room temperature or in a warming bath.

VIII. QUALITY CONTROL PROCEDURES

A. Overview

To assure validity of the results in this study requires rigid adherence to collection, labeling, and shipping protocols. To ensure that these are well understood, a training session will be held to provide training and experience before the beginning of the project. Adherence to these protocols, including periodic reviews and retraining, are the responsibility of each field center.

In addition, other quality control measures will be taken to assess the integrity of the stored samples once they are removed from storage for analysis in addition to individual laboratory quality control programs that are in place for each analyte.

B. Sample Integrity

Aliquots of samples will be frozen upright at -80°C before being placed in boxes for long-term storage and shipping. Upon removal from freezers for shipping or analysis, the sample should be inspected to for evidence of thawing and leaking. If the liquid is no longer frozen (with top of frozen layer being horizontal in the vial) in the bottom of the vial or if there is evidence that the sample has leaked, based on less than the original volume remaining in the vial, the sample will be discarded and replaced by another sample that is acceptable.

Upon receipt at local or central laboratories, samples will be inspected upon unpacking to assure that they remained frozen in transit. Any sample showing evidence of being thawed will be noted. If transportation to the local laboratory occurs immediately upon removal from the -80°C freezer (within three hours) the sample needs to be kept frozen. Any sample that showed evidence of thawing but remained cold during transport may be analyzed for lipids and lipoproteins, but not for coagulation factors. Analysis should occur within three days of receipt of these samples. Any sample that leaked during transport will not be analyzed.

Any sample that has been identified as thawed will not be included in the data analysis if the analytical results are greater than 3SD (biologic plus analytical) from the average of the other three in that set of four.

Expected biologic plus analytical SD for triplicate analysis (Clin. Chem. 36,209, 1990)

	1 SD
Cholesterol	5%
Triglyceride	13%
HDL-chol	7%
Apo A-1	10%
Apo B-100	11%

Sample identity will also be verified based on packing lists and FAXed inventory lists. Any shipment that shows a discrepancy between the packing list and the actual contents may be sent back to the originating center to correct if the discrepancy cannot be resolved by a phone call.

C. Analytical Quality Control Procedures

All analytical runs will include appropriate quality control samples to assure the validity of the run. Quality control samples will be analyzed at specific intervals with each run as specified by the manual of operation for the laboratory performing the analysis. If the quality control materials do not meet the criteria set by the laboratory's manual of operation, the run must be rejected and repeated in total.

D. Longitudinal Control Procedures

To be able to assess comparability of analyses in earlier years and later years for this study, samples other than diet study samples, will be used as not to deplete the archival stores of study subject samples.

Three volunteers were recruited from each center to provide a series of "endpoint" samples which that were treated and aliquoted as a modified endpoint set to provide six sets of vials for each of the core analytes. See Protocol 1.

All field center laboratories will, in addition, participate in the Lipid Standardization Program of the Centers for Disease Control, which provides some control for longitudinal samples of lipoprotein profiles.

IX. DATA RECORDING AND TRANSFER

A hard copy of all results will be retained by all laboratories for the duration of the study. Values from the field center lipid laboratories and the MIBH Lipid Laboratory will be submitted to each field center by FAX, regular mail, or electronically, using predesigned forms. The UV will send hard copy plus data entered on floppy disk.

X. TRAINING PROCEDURES

The purpose of training is to provide standardized methodology for venipuncture and blood processing for the field centers. Standardization of procedures is important for the quality of blood samples from participants

A. Training and Certification.

Field center technician training and certification was carried out as part of Protocol I. A field center coordinator, designated at each field center, is responsible to maintaining the level of competence of field center personnel in the standard procedures. Personnel who participated in the initial training program were certified. Recertification of field technicians takes place prior to each blood-drawing year or when new technicians are enrolled. This training is the responsibility of the field center coordinator.

B. New protocols

New protocols, involving techniques not used in the last protocol, will be introduced by a video prepared by the University of Vermont. These will include the method for filtering the plasma from the Diatube for beta-thromboglobulin assays and the methods for treating platelets for the studies involving flow cytometric analysis.

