In 12a, circle either YES or NO. A change in smoking habits is defined as started smoking, stopped smoking, or increased or decreased smoking by at least 50 percent. If the response to 12a is NO, go to question 13. If the response to 12a is YES, then proceed with 12b and circle one letter only corresponding to the correct response. *(Note to interviewer: If 12a is answered YES, inform the Study Coordinator.)*

Question 13: Women Only *(Answered based on information from the week preceding the first weekly interview.)*

In 13a, circle either YES or NO. If the response to 13a is YES, then proceed with 13b and 13c, recording the date and circling the day of the week the participant began menstruating. *(Note to interviewer: This question should be skipped completely for men participants as well as for clearly postmenopausal women participants. NA is not needed as a response.)*

Reminder to All Study Personnel: Be sure to complete this form for each participant at the time of the last blood draw of the feeding period.

Participant Weekly Monitoring

Form Code: PWM
Version B 5/10/94

DELTA ID: _____

Monday's DATE: ____/____/____
[THIS WEEK] (mm/dd/yy)

1. Code Number of personnel completing this form: _____

BLOOD DRAW

[Complete numbers 2-4 during weeks 5, 6, 7.]

2. Period 1 2 3 [Circle correct number]

3. Week 5 6 7 [Circle correct number]

4. Date of blood draw ____/____/____
mm/dd/yy

WEIGHT [THIS week]

[Participants are weighed before dinner, without shoes or coats.]

5. a. Date of first weekly weight: _____
(mm/dd/yy)

First weekly weight, either in lbs or kg:

b. lbs: _____ or c. kg: _____

d. Current calorie level: 1500 2000 2500 3000 3500 [Circle correct number]

6. a. Date of second weekly weight: _____
(mm/dd/yy)

Second weekly weight, either in lbs or kg:

b. lbs: _____ or c. kg: _____

d. Current calorie level: 1500 2000 2500 3000 3500 [Circle correct number]

Be sure to administer this form at the last blood draw of the period!

Figure 4.5.2: Participant Weekly Monitoring

Participant Weekly Monitoring

Form Code: PWM
Version B 5/10/94

[Interviewer: Ask the participant the rest of the questions based on their activities during the past week.]

EXERCISE [Exercise is recorded at the first weekly visit following the weekend.]

7. a. In the past week, has your exercise level changed? YES NO [If NO go to question 8]
b. If YES, how has your exercise level changed: [Circle letter preceding your selection]

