APPENDIX I

Table 1 Overview of Endpoint Sample Collection

Once per week to give 3 sets per diet period		Twice per diet period	Twice per subject	Once per diet period		
Endpoint package similar to Protocol 1 with six tubes of blood (41 mL)		Urine first AM	Buffy Coat	Platelets Special Prep	Postprandial Regular diet**	Postprandial Fat load**
Citrated plasma	Diatube EDTA plasma*	Urine			12 pm & 5 pm	@ 4 h & 8 h
2x10 mL	5 mL	Urine		Platelets special	Serum**	2 x 7 mL EDTA***
	7 mL				2 x 7 mL	2 x 7 mL Serum**
						2 x 4.5 mL Citrate
14 vials	4 vials (4°)	2 vials	6 vials	5 vials	3 buffys	7 tubes
	4 vials (r.t.)					2 x 2 vials EDTA***
						2 x 4 vials serum
						2 x 3 vials citrate

* Week 5 and 6 only

** Assumes that postprandial studies will take place on the same day as the fasting endpoint sample from that week. One tube of blood of each type will be drawn at each of the two scheduled times and aliquoted to give one set of vials. Since this is done twice in the same day, the need for two samples or vials is indicated as 2 x each tube or vial type.

*** Must be protected from light; stored under nitrogen.

**Table 2 Disposition of samples for testing and archiving
Endpoint tests**

Tests	Per week per diet period						Per person
	serum	citrated plasma 4°	citrated plasma r.t.	Diatube plasma	EDTA plasma	urine buffy	
Lipid profile, glucose	2						
Insulin	1						
Factor VII			1				
Fibrinogen		1					
PAI-1		1					
Apo E genotype							1
LDL size					2		
beta-thromboglobulin				1			
VLDL-cholesterol	1						
HDL-subfractions	2						
Apo A/B	1						
Total used for testing	7	2	1	1	2	0	1
Remainder for archives	7	2	3	1	4	5	5
Possible tests from archives							
Microalbuminuria							1
CRP	1						
Uric acid	1						
Lp(a)	1						

**Table 3 Disposition of samples for testing and archiving
Special tests**

Postprandial (Regular diet)	Serum (12 pm & 5 pm)	EDTA plasma (4 & 8 h)	Citrated plasma (4 & 8 h)
Triglycerides, glucose	1		
Insulin	1		
Total for testing	2		
Total for archives	2		
Postprandial (Fat load)	Serum (4 & 8 h)	EDTA plasma (4 & 8 h)	Citrated plasma (4 & 8 h)
Triglycerides, glucose	1		
Insulin	1		
Retinyl palmitate		1	
Total for tests	2	1	0
Total for archives	2	1	3

Platelets

7 tubes per diet; all will be analyzed; no archives

Table 4 Summary of Locations for Laboratory Testing and Test Volume

TEST	SITE	TEST SCHEDULE	
		tests/diet phase	timing (week #)
Lipid Profile	Local Lab	3	5,6,7
Glucose	Local Lab	3	5,6,7
Insulin	MIB	3	5,6,7

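### The rule for dropping thawed samples needs a set of four results that does not exist (each diet yields three or two), leaves its SD undefined, and lets the measured value decide what is kept

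*Protocol*

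**What the plan says.** The rule is in Chapter 8, VIII.B. It begins "Any sample that has been identified as thawed will not be included in the data analysis if the" and continues "analytical results are greater than 3SD (biologic plus analytical) from the average of the other three in that set of four". A short table of SDs follows, headed "Expected biologic plus analytical SD for triplicate analysis": cholesterol 5%, triglyceride 13%, HDL-C 7%, apo A-1 10%, apo B-100 11%.

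The same section has two other provisions on thawing. A vial found unfrozen or leaked when taken from the freezer, whether for shipping or for analysis, is discarded and replaced with an acceptable one. A sample found thawed at receipt is noted. If it stayed cold in transit it may be assayed for lipids and lipoproteins, within three days, but not for coagulation factors.

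On the number of draws, Chapter 8, II.A says "DELTA Study requires collection of approximately 41 ml of blood three times at the end of each diet phase". Table 1 of Appendix I says "Once per week to give 3 sets per diet period". The weekly monitoring form in section 4.5 says "Complete numbers 2-4 during weeks 5, 6, 7". Table 4 lists "Lipid Profile Local Lab 3 5,6,7" and gives apo A-1 and apo B the same schedule, but gives LDL size, VLDL-C and HDL subfractions two determinations, at weeks 6 and 7. Section 1.0.2 makes LDL size a primary lipid endpoint.

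**The concern.** A rule that excludes data has to be executable and should not depend on the result it is screening. This one falls short in three ways.

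- **Set size.** It calls for three comparators, and the protocol supplies two or one.
- **Limit.** The yardstick is an SD of unstated basis, and it is absent for several lipid endpoints that the rule would govern.
- **Dependence on the result.** Among thawed samples, the measured value alone decides whether the sample stays. A vial with the same defect found at the freezer is replaced whatever its value would have been.

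Each laboratory would have to improvise. The choices it makes change both how many sound values are lost and how many altered ones remain, in endpoints that include the primary lipids.

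**Working it through.** **Can a set of four be found?** The supply list in Chapter 8, Appendix III gives vials per participant, and the processing tables give vials per draw. With three diets:

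| Tube | Vials per participant ÷ vials per draw | Draws | Draws per diet |
|---|---|---|---|
| Serum | 126 / 14 | 9 | 3 |
| Citrate, cold | 36 / 4 | 9 | 3 |
| Citrate, room temperature | 36 / 4 | 9 | 3 |
| EDTA | 54 / 6 | 9 | 3 |
| Diatube | 12 / 2 | 6 | 2 |

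This agrees with II.A, Table 1, Table 4 and the weekly form. No source gives four.

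Four aliquots of one draw is not a workable reading either. A serum draw gives 14 vials. Where one tube does give four vials (citrate, postprandial serum), Tables 2 and 3 send only some for testing and archive the rest, so there are no four results to average. The limit also includes biologic variation, which only makes sense between draws.

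**Comparators available.** Lipid profile and apo A-1/B: 3 − 1 = 2. LDL size, VLDL-C and HDL subfractions: 2 − 1 = 1.

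**Chance that an undamaged thawed sample is dropped.** Let σ be the single-draw SD and assume independent, normally distributed draws. The difference between one draw and the mean of k others has SD σ√(1 + 1/k).

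- If the tabled SD is σ: P = 2[1 − Φ(3/√(1 + 1/k))].
- If the tabled SD is that of a mean of three, σ/√3: the limit is √3·σ and P = 2[1 − Φ(√3/√(1 + 1/k))].

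| k | Tabled SD is for one draw | Tabled SD is for a mean of three |
|---|---|---|
| 3 (as written) | z = 2.598, 0.94% | z = 1.500, 13.4% |
| 2 | z = 2.449, 1.4% | z = 1.414, 15.7% |
| 1 | z = 2.121, 3.4% | z = 1.225, 22.1% |

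Moving from three comparators to two or one matters modestly. The reading of the SD heading matters far more: 15.7/1.4 is about 11-fold and 22.1/3.4 about 6.5-fold.

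**Chance that a shifted sample is kept.** For a shift of δ single-draw SDs, P(kept) = Φ((3 − δ)/√(1 + 1/k)) − Φ((−3 − δ)/√(1 + 1/k)).

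| Shift | k = 2 | k = 1 | Size for triglyceride (SD 13%) |
|---|---|---|---|
| 1 SD | 94.8% | 91.9% | 13% |
| 2 SD | 79.3% | 76.0% | 26% |
| 3 SD | 50% | 50% | 39% |

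**The case against.** The strongest reply is that this is a wording slip in a narrow rule that already has safeguards. Thawed samples cannot be used for coagulation factors, leaked ones are not assayed, only samples that stayed cold may be run, and vials found thawed at the freezer are replaced. What remains is lipid and lipoprotein samples noted as thawed at receipt. All of this stands and limits the weight of the point. It does not make the rule usable for those samples.

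Four stronger readings are tempting, and the documents do not support them.

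- **That a triglyceride change below 39% would never be caught.** The limit applies to an observed difference that includes sampling noise. With two comparators and a single-draw SD, a 26% shift is excluded about 21% of the time (1 − 0.793).
- **That 1.4% or 15.7% of the trial's values would be lost.** These are percentages of samples noted as thawed, and no thaw frequency is given. Nor can the limit be called wide while quoting 15.7%: if 13% is the SD of a mean of three, the single-draw SD is 13% × √3 = 22.5%, and 39% is only about 1.7 of those.
- **That diet contrasts are biased.** Section 4.3 masks the sites' laboratory technicians. Under Table 7 the endpoint samples other than platelets ship after Period 3, and VII.B has them bagged by subject, so a warmed package would tend to affect all of a subject's diets. The same arrangement could thaw the comparison draws too, which weakens the rule as a detector. Nor do the documents show that a lipid sample thawed cold is degraded.
- **That the missing SDs for glucose and insulin are a serious gap.** The permission to assay thawed samples names only lipids and lipoproteins.

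**Conclusion.** The contradiction is certain: the rule names a set of four, and every count in the protocol gives three draws, with two determinations for LDL size, VLDL-C and HDL subfractions. The rule cannot be applied as written. Its SD basis is undefined, and it is missing for LDL-C, LDL size, VLDL-C and HDL subfractions. Keeping or dropping a thawed sample depends on its own result.

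Among thawed samples, wrongful exclusion runs from 1.4% to 22.1%, depending on the number of comparators and the meaning of the SD. With a single-draw SD, most shifts below 3 SD are kept. These figures assume independent, normal draws. The cited source of the SDs might settle which basis applies, but the protocol does not say. The effect on any endpoint or diet contrast cannot be quantified, and differential bias between diets is unlikely. The point merits correction because the rule governs primary lipid endpoints and a simpler rule already exists in the same section.

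**What to change.** Delete the 3-SD sentence. Extend the existing replace-on-thaw rule to lipid and lipoprotein samples noted as thawed at receipt: request an archived serum or EDTA aliquot of the same draw. If none is usable, set the value to missing on thaw status alone, logged before assay and masked to diet. Field-center storage was chosen partly for this: "This reduces the risk of loss of endpoint samples, since some samples would be retained by the Field Centers".

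At minimum, restate the rule for sets of three and of two, say whether each SD is for one draw or a mean, and give one for every analyte covered.

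The cost is archive material. Table 2 leaves 7 serum and 4 EDTA vials per draw. Replacing LDL size takes 2 EDTA. Replacing every lipid and lipoprotein serum vial of a week 6 or 7 draw takes 2 + 1 + 2 + 1 = 6 (lipid profile, VLDL-C, HDL subfractions, apo A/B), leaving 1, although Table 2 lists three possible archive tests on serum (CRP, uric acid, Lp(a)). A thaw in transit could involve a whole mailer, and VIII.D shows that the study wants to avoid depleting its archive. A few values may become missing.
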